Study Rationale	
One third of adults age 65 and older fall annually with 20-30% of falls resulting in serious injuries. In 2009 alone, falls in older adults resulted in nearly 2.2 million emergency room visits. In 2000, direct medical cost of non-fatal falls in adults over age 65 was \$19 billion, and in 2007 that cost was projected to increase to \$54.9 billion/year by 2020. However, despite considerable efforts, falls rates over this time have been highly resistant to change. Thus, there is a critical need for more effective diagnostic efforts to identify older adults at risk of falls and rehabilitative efforts to successfully mitigate that risk once identified. Consistent with studies on the postural control of standing, our recent findings suggest that older adults prioritize visual feedback to control balance in walking.
 
Accordingly, older adults are more susceptible than young adults to optical flow perturbations applied in the safety of virtual reality (VR). These perturbations elicit the visual perception of walking instability, and provide the opportunity to practice walking balance corrections in a controlled environment. The purpose of this proof of concept study is to investigate the propensity for time-dependent tuning of walking balance control and the presence of aftereffects in older adults following a single session of optical flow perturbation training.

Study Objective(s)	To investigate the propensity for time-dependent tuning of walking balance control and the presence of aftereffects in older adults following a single session of optical flow perturbation training.
Test Article(s) (If Applicable)	Mediolateral (ML; i.e., side-to-side) optical flow perturbations applied during treadmill walking using a projection-based virtual reality system.
Study Design	A randomized, crossover design that included a control session of normal unperturbed walking and an experimental session that incorporated mediolateral optical flow perturbations during walking.
Subject Population	Inclusion Criteria
key criteria for Inclusion and Exclusion:	
 1. Subjects Age 65+ years 2. Be able to walk without an assistive aid (i.e., walker, cane) 3. Have the full capacity to provide informed consent
	Exclusion Criteria
	
 1. Current lower extremity injury or fracture 2. Taking medication that causes dizziness 3. Have a leg prosthesis 4. Prisoners 5. Individuals lacking the capacity to provide informed consent

Number of Subjects	Up to 20
Study Duration	
Each subject will participate in two sessions, each lasting up to three (3) hours and separated by at least one week.
 
The entire study is expected to last two years (approximately one year for data collection and another one year for data analysis)

Study Phases	
Screening	(1) Screening : We will use an initial telephone screening (attached) to evaluate basic study eligibility. Subjects that meet inclusion/exclusion criteria following phone screening will be invited to participate in the study.
Study Treatment	
Follow-Up	(2) Balance training : Subjects that provide written informed consent will participate in the cross-over design that includes one control session and one session of perturbation training, separated by at least one week.
Efficacy Evaluations	
Primary outcome measures:
 
(1) Change in Postural Sway
 
(2) Change in kinematic (step width) variability
 
(3) Change in foot placement targeting accuracy
 
Secondary outcome measures:
 
(1) Change in Cognitive-motor Interference Accuracy
 
(2) Change in Cognitive-motor Interference Response Time After 10 Min of Walking
 
(3) Change in Margin of Stability Variability After 10 Min of Walking

Statistical Analysis Plan	A one-way, repeated-measures analysis of variance will test for effects of time on dependent variables collected from each session. Significance will be defined using an alpha level of 0.05.
DATA AND SAFETY MONITORING PLAN	This study does not meet the criteria for an independent DSMP. The PI ([name]) will oversee all conduct to ensure the safety of all participants and the integrity of the data. At least one research staff member will be monitoring the subjects' movement patterns during the data collection. If the subject experiences any discomfort, the data collection will be stopped immediately. If any member of the research team encounters unanticipated problems (including but not limited to adverse events), we will make necessary adjustments to the protocol and, where appropriate, report these events to University administrative personnel.

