2 STUDY OBJECTIVE

The purpose of this proof-of-concept study is to evaluate change in walking balance in older adults responding to a single session of optical flow perturbation training compared to a control session of normal walking.

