2.1 Primary Objective

Quantify the time-dependent changes in metrics of walking balance in older adults after walking with optical flow perturbations.

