2.2 Secondary Objective

Contrast effects of walking with optical flow perturbations to those of normal treadmill walking.

3 INVESTIGATIONAL PLAN (brief overview)

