3.3 Study Population

Inclusion Criteria:

1. Subjects Age 65+ years
2. Be able to walk without an assistive aid (i.e., walker, cane)
3. Have the full capacity to provide informed consent

Exclusion Criteria:

1. Current lower extremity injury or fracture
2. Taking medication that causes dizziness
3. Have a leg prosthesis
4. Prisoners
5. Individuals lacking the capacity to provide informed consent

4 STUDY PROCEDURES (what will be done)

Subjects will be comfortably fit with a safety harness and instructed on all safety procedures. Subjects will then walk at their preferred speed on a force-sensing treadmill for 5 min to acclimate to the equipment and allow their movement patterns to stabilize.

Subjects will then complete a block protocol design with pre and post measurements separated by up to 20 min of normal treadmill walking (Session A) or in the presence of optical flow perturbations (Session B). Pre and post measurements will include baseline measurements during normal walking and:

- 1) Foot placement targeting task. Subjects will be exposed to a series of footprint targets intermittently projected onto the treadmill belt. Subjects will be asked to direct their feet to the target with their next step as accurately as possible.
- 2) Auditory 'Stroop' task. While wearing headphones with a microphone, subjects will hear the words high and low in pitches that are either high or low and asked to verbally identify the pitch of those words as quickly as possible.

Subject Completion/ Withdrawal procedures

If subjects are unable to complete the protocol or suffer a musculoskeletal injury before or during the time period when they are involved in the study, they will be withdrawn from the study.

5 STUDY EVALUATIONS AND MEASUREMENTS (how measurements will be made)

3D motion capture and an instrumented treadmill will record the position and orientation of body segments and joints and ground reaction forces. Using custom software, we will compute the mean and standard deviation of step width variability, postural sway variability, and margin of stability variability. The outcome measure from the foot placement targeting task will be foot placement accuracy. The outcome measures from the auditory Stroop task will be cognitive-motor interference accuracy and response time. Efficacy measurements will be made using the change in each outcome measure after walking normally or with optical flow perturbations.

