6 STATISTICAL CONSIDERATION

Sample size is based on our published estimates of age-related differences in balance outcome measures. n=14 subjects per group would have 90% power to detect ($p<0.05$) a difference in dynamic instability during visually perturbed walking between healthy older (1.38 ± 0.20 , unitless) and healthy young (1.20 ± 0.10 , unitless) adults (Franz et al., 2015). This number of subjects would also sufficiently power our detecting differences in step width variability (8.92 ± 1.00 vs. 4.02 ± 0.96) (Francis et al., 2015).

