6.1 Statistical Methods

A two-way rmANOVA will test for significant main effects and interactions between time (Pre versus Post) and experimental session (perturbations versus normal walking). Significance will be defined for each main effect using an alpha level of 0.05.

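### The synopsis and section 6.1 plan different analyses, and the time × session interaction, the only test of whether change differs between perturbed and normal walking, has no stated alpha or role

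*Combined protocol and SAP*

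**What the plan says.** **Synopsis, Statistical Analysis Plan row.** "A one-way, repeated-measures analysis of variance will test for effects of time on dependent variables collected from each session". A general alpha of 0.05 follows. There is no session factor, and the time levels are not defined.

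**Section 6.1.** "A two-way rmANOVA will test for significant main effects and interactions between time (Pre versus Post) and experimental session (perturbations versus normal walking"). The next sentence reads: "Significance will be defined for each main effect using an alpha level of 0.05". The interaction is listed as something to be tested, but the alpha sentence does not mention it.

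**Objectives.** Section 2 gives the purpose as change in walking balance in older adults "responding to a single session of optical flow perturbation training compared to a control session of normal walking"; section 1.1 says the same. Section 2.1 (primary) is: "Quantify the time-dependent changes in metrics of walking balance in older adults after walking with optical flow perturbations". Section 2.2 (secondary) is: "Contrast effects of walking with optical flow perturbations to those of normal treadmill walking".

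**Efficacy measure, section 5.** "Efficacy measurements will be made using the change in each outcome measure after walking normally or with optical flow perturbations".

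The documents do not say which of the two analyses governs, whether one follows up the other, or which objective each serves.

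**The concern.** The one-way test can serve objective 2.1, which concerns change after perturbed walking. It cannot serve objective 2.2 or the overall purpose, because it never compares the sessions.

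The two-way model can make that comparison, but only through its interaction. The time main effect averages the pre-post change over both sessions. The session main effect averages pre and post values within each session. Neither shows whether the change differs between sessions.

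Both sessions repeat the foot-targeting and auditory Stroop tasks around up to 20 minutes of treadmill walking, so habituation, task practice or fatigue could move the outcomes in either session. The control session is there to separate such shared change from an effect of the perturbations. If the synopsis analysis or the main-effect rule is followed as written, a shared change could be credited to the perturbations.

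**Working it through.** **1. The plan's own figure.** Section 6 gives 14 per group for 90% power at p<0.05, older (1.38, SD 0.20) versus young (1.20, SD 0.10).
- Difference = 1.38 − 1.20 = 0.18. Pooled SD = √((0.20² + 0.10²)/2) = 0.158. Standardized difference = 0.18/0.158 = 1.14.
- One-sided 0.05 (t test): n = 14 per group, power 90.1%. This reproduces the figure.
- Two-sided 0.05 (t test): n = 18 per group, and power at n = 14 is 82.6%. This does not reproduce it.

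Either way the figure is for a comparison of age groups ("Sample size is based on our published estimates of age-related differences in balance outcome measures"). It sizes neither the time effect nor the interaction.

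**2. What each test estimates.** Let D_A and D_B be one subject's post-minus-pre change after normal walking (Session A) and perturbed walking (Session B).
- One-way test in a session (taking two time levels): paired t on D_A or on D_B.
- Time main effect: t on (D_A + D_B)/2.
- Time × session interaction: t on D_B − D_A.

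Only the last has expectation zero when both sessions produce the same change.

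**3. Effect of a shared change.** Assumptions, not document figures: D_A and D_B are bivariate normal with the same mean *d*, SD 1 and correlation *r*; all tests are two-sided at 0.05. The sample sizes are 20 (the enrolment ceiling) and 14 (the section 6 figure). Results are from 200,000 simulated trials per scenario.

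| n | d (SD) | r | B significant, A not | Time main effect significant |
|---|---|---|---|---|
| 20 | 0.45 | 0 / 0.5 / 0.7 | 25% / 17% / 13% | 77% / 60% / 54.5% |
| 20 | 0.30 | 0 / 0.5 / 0.7 | 19% / 13% / 10% | 44% / 31% / 28% |
| 14 | 0.45 | 0 / 0.5 / 0.7 | 22.5% / 16% / 12% | 60% / 44% / 39% |

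The interaction is significant in 5% of trials in every scenario.

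Analytic check on the time main effect: (D_A + D_B)/2 has SD √((1 + r)/2), so the noncentrality is d√n / √((1 + r)/2). For n = 20, d = 0.45, r = 0.5 this is 0.45 × 4.472 / 0.866 = 2.32. The noncentral t on 19 df then gives 59.7%, in line with the simulated 60%.

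**4. What the interaction can detect.** For 80% power (paired t, two-sided 0.05), the mean of D_B − D_A must be 0.66 of its own SD at n = 20, or 0.81 at n = 14. That SD is √(2(1 − r)) in units of one session's change. At n = 20 the requirement becomes:
- r = 0: 0.66 × 1.414 = 0.93 SD
- r = 0.5: 0.66 × 1.000 = 0.66 SD
- r = 0.7: 0.66 × 0.775 = 0.51 SD

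The documents give no SD of change, so these cannot be converted to outcome units.

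**The case against.** **The right test is already planned.** Section 6.1 says interactions will be tested, and 0.05 is the only significance level in the documents, so a reader would infer it. Section 2.2 gives the contrast a secondary role by implication. This stands, and it limits the severity: no analysis is missing. But the rule in 6.1 is written for main effects only, and the general alpha in the synopsis belongs to a model with no interaction.

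**The two analyses may be complementary,** the one-way test serving 2.1 and the two-way model serving 2.2. That is a sensible reading, but the documents do not state it.

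**The harm depends on a rule of inference the plan never states.** No section says that significance in one session only, or a time main effect, will be credited to the perturbations. This is correct. The rates above are not type I errors, and the time-main-effect rates are simply power to detect a change assumed to be real. The exposure arises because the plan does not rule that reading out.

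**The leading scenario is close to the worst case.** With r = 0 the one-session-only rate is p(1 − p), where p is the power in one session. Here p = 0.48, so 0.48 × 0.52 = 0.25, the maximum. At n = 20 and r = 0 the rate is about 7% for a shared change of 0.1 or 0.8 SD and about 1% at 1.0 SD. This stands for that pattern. It does not apply to the time main effect, whose rate keeps rising with the shared change.

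**The 5% for the interaction is per outcome.** There are three primary and three secondary outcomes. If they were independent, the chance of at least one false positive would be 1 − 0.95³ = 14% for three and 1 − 0.95⁶ = 26% for six. This is true, but it is a separate matter that naming the interaction neither causes nor cures.

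**Conclusion.** The concern holds and should be fixed. The synopsis and section 6.1 specify different models with no order between them, and the synopsis model cannot answer the study's stated comparison. Section 6.1 contains the test that can, but its decision rule leaves that test out.

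For a shared change of 0.3 to 0.45 SD and correlations of 0 to 0.7 at n = 20, a pattern open to misreading as a training effect appears in 10% to 25% of trials (significant after perturbation only) or 28% to 77% (time main effect), against 5% for the interaction. The range rests on assumed changes and correlations. The conclusion that the two texts must be reconciled and the interaction given a role does not depend on it.

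**What to change.** Use the two-way time × session model in both the synopsis and section 6.1, and add wording such as:

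> *Any claim that perturbation training differs from normal walking rests on the time × session interaction (the within-subject difference between sessions in pre-post change), two-sided alpha 0.05. Objective 2.1 is addressed by the pre-post change within the perturbation session, reported with its 95% CI. That change, the main effects, and a pattern of significance in one session but not the other are not used to attribute change to the perturbations.*

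If the one-way test in the synopsis is meant to describe a time course within a session, say so and define its time levels.

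**Cost.** Wording in two places. No new data or subjects are needed, and the ranking of objectives 2.1 and 2.2 is unchanged. The downside is that fewer effects can be called training effects. Because the study was not sized for the interaction, a non-significant result should be reported with its CI and not read as no effect.

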1 BACKGROUND AND RATIONALE

1.1 Introduction

Older adults are at an exceptionally high risk of debilitating falls, contributing significantly to reduced independence and quality of life. Despite conventional diagnostic and rehabilitative efforts, one-third of people over age 65 fall annually and 20-30% of these falls lead to moderate to severe injury. When adjusted for inflation, annual direct medical costs from non-fatal falls in older adults are expected to reach \$67.7 billion by 2020. Moreover, three decades of falls prevention research have led to present guidelines that include recommendations for targeted exercise interventions. However, most of the programs evaluated during this time only modestly influenced the sizeable portion of our aging population experiencing one or more falls annually. Unfortunately, our society now faces a growing dilemma – evidence suggests that the rate of injurious falls is accelerating, with 2.4 million emergency department visits in 2011, up 46% from 2001 despite only a 17% increase in the older adult population.

There is a growing appreciation that interventions designed to challenge balance are those most likely to have positive impact on balance integrity. Unfortunately, conventional interventions based on this premise elicit only modest improvements unlikely to impact the high prevalence of falls. Our research group is at the forefront of using optical flow perturbations applied during walking in the safety of virtual reality (VR) to elicit the visual perception of instability during walking. The purpose of this proof-of-concept study is to evaluate change in walking balance in older adults responding to a single session of optical flow perturbation training compared to a control session of normal walking.

1.2 Name and Description of Investigational Product or Intervention

Optical flow perturbation system and paradigm: Subjects walk on a treadmill surrounded by a semicircular curved screen on which a speed-matched virtual hallway is projected. To this motion, the system adds pseudo-random mediolateral (ML, side-to-side) oscillations of the virtual hallway, designed to elicit the visual perception of lateral instability.

A. Optical flow perturbations are designed to target visual dependence and walking balance deficits in PwMS.

B. Our original work revealed age-related differences in walking balance control that were not apparent during normal, unperturbed walking.

[figure not shown]

Figure 1. System and disproportionate effects in older versus young adults.

1.3 Relevant Literature and Data

The investigators have a significant history of testing the effects of optical flow perturbations on walking balance in young and older adults and in patients with multiple sclerosis. Our cumulative evidence from these studies (listed below) demonstrate that older adults are significantly more susceptible to these perturbations than young

adults (Fig. 1). Accordingly, we now know that this environment uniquely disrupts walking balance in older adults, thereby providing an opportunity to “practice” corrective motor adjustments relevant to preserving balance.

2 STUDY OBJECTIVE

The purpose of this proof-of-concept study is to evaluate change in walking balance in older adults responding to a single session of optical flow perturbation training compared to a control session of normal walking.

2.1 Primary Objective

Quantify the time-dependent changes in metrics of walking balance in older adults after walking with optical flow perturbations.

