3.1 Study Design

(Session A: Normal walking, Session B: Continuous optical flow perturbations). In a randomized cross-over designed (assigned at enrollment using a random number generator), subjects will walk normally (session A) and be exposed to continuous side-to-side motions of the virtual hallway (Session B). These walking trials will last up to 20 min and will be separated by at least one week.

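### The primary objective names no comparator and the randomised contrast with normal walking is ranked second; the planned time-by-session interaction should be named as the test for the primary outcomes

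*Combined protocol and SAP*

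**What the plan says.** Section 2 describes the study as evaluating change in walking balance in older adults "responding to a single session of optical flow perturbation training compared to a control session of normal walking". Section 1.1 states the same comparative purpose.

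The ranked objectives read differently:
- Primary (Section 2.1): "Quantify the time-dependent changes in metrics of walking balance in older adults after walking with optical flow perturbations".
- Secondary (Section 2.2): "Contrast effects of walking with optical flow perturbations to those of normal treadmill walking".

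The design is a two-session crossover with random assignment (Section 3.1). In each session, Pre and Post measurements are separated by up to 20 min of walking, and the foot placement targeting task and the auditory Stroop task are done at both times (Section 4). Five minutes of treadmill walking to acclimate come before the Pre measurement.

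The synopsis lists the primary outcomes only as changes, for example "1) Change in Postural Sway", without saying which contrast of changes is meant. The analysis is given twice:
- Synopsis: "A one-way, repeated-measures analysis of variance will test for effects of time on dependent variables collected from each session".
- Section 6.1: "A two-way rmANOVA will test for significant main effects and interactions between time (Pre versus Post) and experimental session (perturbations versus normal walking").

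Section 6.1 then sets the 0.05 level for main effects and gives none for the interaction.

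**The concern.** The crossover pays for a control session so that whatever happens to anyone who walks on a treadmill and repeats the tasks can be subtracted out. A primary objective that concerns Session B alone does not use that control. Two influences are present in both sessions and can move a Pre-Post change without any perturbation effect: practice on repeated tasks, and fatigue over up to 20 min of walking. Practice matters directly, because foot placement targeting accuracy is one of the three primary outcomes. The Stroop measures are secondary outcomes.

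If the primary claim is read from the Session B change, shared improvement could be reported as tuning or an aftereffect of the perturbations, and shared worsening could hide a real benefit. The time main effect in Section 6.1 has the same weakness, because it averages the two sessions and does not contrast them.

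**Working it through.** **1. Which planned test answers which objective**

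| Test | Where planned | Removes drift common to both sessions? |
|---|---|---|
| Effect of time, Session B alone | Synopsis | No |
| Time main effect, both sessions averaged | Section 6.1 | No |
| Time-by-session interaction | Section 6.1 | Yes |

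With two levels of each factor, the interaction is the paired t-test on Session B change minus Session A change. The Section 2 purpose and the Section 2.2 objective need the third row. Section 2.1 as worded is met by the first. No section links the primary outcomes to one row.

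**2. The plan's own sample size figure**

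Section 6 gives n=14 per group for 90% power, comparing older (1.38, SD 0.20) with young (1.20, SD 0.10) adults. The pooled SD is √((0.20² + 0.10²)/2) = 0.158, so the standardised difference is 0.18/0.158 = 1.14. By the noncentral t, power at 14 per group is 90.1% with one-sided 0.05 and 82.6% with two-sided 0.05. The figure therefore reproduces only one-sided. More to the point here, it concerns a difference between age groups and so supports neither a Pre-Post change nor a difference between sessions.

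**3. What shared drift would do**

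Assumptions, since the documents give no drift and no SD of change: the perturbations have no effect; both sessions have the same mean Pre-Post drift δ, in SD units of a single-session change; change scores are normal; tests are two-sided at 0.05. N is 14 (Section 6) or 20 (the enrolment ceiling). ρ is the correlation between a subject's two changes.

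- Session B alone: one-sample t, df = N−1, noncentrality δ√N. For δ=0.5 and N=20 this is 0.5 × 4.472 = 2.236.
- Time main effect: the mean of the two changes has variance (1+ρ)/2, so noncentrality is δ√N/√((1+ρ)/2); ρ=0.5 is assumed.
- Session B minus Session A: δ cancels, so noncentrality is 0.

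Chance of a significant result:

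| δ | Session B alone, N=14 | Session B alone, N=20 | Time main effect, N=14 | Time main effect, N=20 | B minus A |
|---|---|---|---|---|---|
| 0.1 | 6.4% | 7.1% | 6.9% | 7.8% | 5% |
| 0.25 | 14.0% | 18.6% | 17.1% | 23.2% | 5% |
| 0.5 | 41.0% | 56.5% | 51.6% | 68.8% | 5% |
| 0.8 | 79.0% | 92.4% | 89.1% | 97.5% | 5% |

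Simulation with 40,000 runs per setting agreed; the interaction was significant in 4.9% to 5.2% of runs.

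The reverse case: a true benefit of 0.8 SD with a shared worsening of 0.5 SD leaves a net Session B change of 0.8 − 0.5 = 0.3 SD, which Session B alone detects with about 25% power at N=20.

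**4. What the controlled contrast costs in power**

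The difference of two changes has SD √(2(1−ρ)) in the same units, so a perturbation-specific effect of 0.8 becomes 0.8/√(2(1−ρ)): 0.566, 0.676 and 0.8 for ρ = 0, 0.3 and 0.5. With no drift:

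| | B minus A, ρ=0 | ρ=0.3 | ρ=0.5 | Session B alone |
|---|---|---|---|---|
| N=20 | 67% | 82% | 92% | 92% |
| N=14 | 50% | 65% | 79% | 79% |

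**The case against.** The strongest reply is that the controlled comparison is already there: Section 2 is comparative, and the only method in the body of the protocol includes the interaction. That stands. A reader might infer that the trial has no controlled analysis, and Section 6.1 shows otherwise. What is missing is a statement that the interaction answers the primary question.

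A reader might also infer that the uncontrolled change decides the trial, or that practice alone will make the primary result positive. The documents do not support either. Section 2.1 sets out to quantify, not to test, and no section gives a success rule or a testing order. A significance claim on Session B alone arises only if the synopsis analysis is used for the primary outcomes; the Section 6.1 time main effect could be misread in the same way. The plan permits these routes and does not prescribe them.

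Describing the response first and contrasting it second is a recognised order in proof-of-concept work, and the synopsis objective of tuning and aftereffects is itself worded without a comparator. This is fair as long as attribution to the perturbations rests on the contrast, which the plan does not say.

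The acclimation period is a real mitigation, but it lessens only that route and not task practice or later fatigue. Fatigue would more plausibly worsen balance than imitate a benefit, so its likelier harm is to mask one.

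Finally, the percentages depend wholly on the assumed drift; at 0.1 SD the inflation is small.

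**Conclusion.** The concern holds as a mismatch of ranking and naming. The stated purpose is comparative, the primary objective is not, and the one planned test that serves the purpose is not tied to the primary outcomes or given a significance level. Following the plan as written could therefore credit shared practice to the perturbations, or let shared fatigue hide their effect. The size cannot be fixed from the documents. Over assumed drifts of 0.1 to 0.8 SD, the Session B test would be falsely significant in roughly 6% to 79% of trials at N=14 and 7% to 92% at N=20, against 5% for the contrast. The 5% rests on the mean drift being equal in the two sessions. The change is worth making because it is cheap and restores the sponsor's own purpose, not because the bias has been shown to be large.

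**What to change.** - **Section 2.1:** make the primary objective the comparison, within subject, of the Pre-to-Post change after perturbed walking with that after normal treadmill walking (Session B minus Session A).
- **Section 2.2:** keep the Session B change as a secondary, descriptive objective, reported with a 95% confidence interval and not used alone to claim a training effect.
- **Section 6.1:** name the time-by-session interaction, at alpha 0.05, as the test for each primary outcome.
- **Synopsis:** replace the per-session one-way analysis with the Section 6.1 analysis, and state that each primary outcome is the between-session difference in change.

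This is a wording change to a model already planned, with no new visits or measurements. The price is lower nominal power when the two sessions' changes are weakly correlated: for the 0.8 SD effect above, 50% to 79% at N=14 and 67% to 92% at N=20, with no loss against the uncontrolled test at a correlation of 0.5. The n=14 statement in Section 6 should not be cited as power for this contrast. A proper statement needs the SD of the within-subject difference in change, which the documents do not give.
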